4.8.4.1 Analysis of AQLQ(S)+12

The overall and 4 domain scores (symptoms, activity limitations, emotional function, and environmental stimuli) from the AQLQ(S)+12 responses along with their respective changes from baseline will be summarized using descriptive statistics. The change from baseline in the overall AQLQ(S)+12 score will be analyzed. Additionally, the proportion of AQLQ(S)+12 responders will be reported; subjects with ≥ 0.5 improvement and subjects

with \geq 1.5 improvement from baseline in AQLQ(S)+12 scores at each visit will be reported separately.

4.8.4.2 Analysis of EQ-5D-5L

The responses from each dimension (mobility, self-care, usual activities, pain/discomfort, and anxiety/depression) and the visual analog scale will be summarized by treatment group and visits. The shift tables will be provided for each dimension. The change from baseline in visual analog scale will be summarized with descriptive statistics by visit.

4.8.5 Safety

This will be assessed by summarizing AEs and SAEs using the as-treated population. Other variables used for the safety assessments include but are not limited to ECG, vital signs, and routine laboratory assessments, which will be evaluated in the MEDI9929 and placebo groups as changes from baseline. These variables as well as their changes from baseline will be summarized descriptively. In addition, shift tables will be included.

4.8.5.1 Analysis of Adverse Events

The occurrence of both treatment-emergent and non-treatment-emergent AEs and SAEs will be described by system organ class (SOC), preferred term, severity, and relationship to the investigational product. Related TEAEs/TESAEs are those events in which the investigator has assessed the relationship to investigational product as related. Subjects will be counted only once for each preferred term, once for each SOC, and by the highest severity of an event, regardless of how many instances of that event the subject experienced. Number of subjects with elevated liver function tests that meet the Hy's law definition will be summarized and evaluated. Verbatim terms will be coded to a standardized preferred term using the Medical Dictionary for Regulatory Activities, the AE classification dictionary endorsed by ICH.

4.8.5.2 Analysis of Clinical Laboratory Parameters

Hematology, serum chemistry, and urinalysis parameters (see Section 4.3.4) as well as their toxicity grade will be summarized with descriptive statistics by treatment group and visit. A shift table will also be provided for these clinical laboratory parameters by treatment group and visit.

4.8.5.3 Analysis of Electrocardiograms

The number of subjects with clinically significant abnormal ECG results based on investigators' judgments will be summarized by treatment group and visit for all subjects.

For the ECG sub-study (approximately 160 subjects), the 12-lead ECG results, QTc intervals (millisecond), will be summarized descriptively by treatment group and visit. Changes from baseline will be summarized into 3 categories: increase \leq 30 millisecond, 30 millisecond < increase \leq 60 millisecond, and increase > 60 millisecond by treatment group and visit. On Day 1, ECGs will be performed in triplicate; the average of these 3 reads will be used as baseline value. Shift tables for QTc intervals (QTc \leq 450 millisecond, 450 < QTc \leq 480 millisecond, 480 millisecond < QTc \leq 500 millisecond, QTc > 500 millisecond) will be presented to compare the baseline ECG evaluation and the post-dose evaluations.

4.8.5.4 Analysis of Vital Signs

Vitals signs will be summarized by treatment group and visit. Pre-dose vital sign change from baseline to post-dose evaluations will also be summarized by treatment group and visit.

4.8.6 Analysis of Pharmacokinetics and Immunogenicity

MEDI9929 serum concentrations will be tabulated by treatment group along with descriptive statistics. Mean and individual serum MEDI9929 concentration-time profiles by treatment group will be plotted. Population PK modeling may be performed to better characterize the PK of MEDI9929 given by SC injection in asthmatic subjects. Potential correlation between PK exposure and PD biomarker, efficacy/safety response may be evaluated.

The incidence rate of positive antibodies to MEDI9929 will be reported by treatment group. If there is a high incidence of ADA, the association of ADA with MEDI9929 concentration will be assessed. In addition, the relationship between ADA and PD, efficacy, and safety may be evaluated.

4.8.7 Stage I, Stage II and Interim Analyses

Two formal analyses (Stage I analysis and Stage II analysis) and an interim analysis are planned for the study.

The Stage I analysis will be conducted after approximately 552 subjects have completed the Week 52 visit. During the Stage I analysis, all the efficacy and safety data collected through Week 52 will be analyzed. Study site personnel and the subjects will remain blinded to the treatment assignment until the end of follow-up period (Week 64). The primary analysis for which the study is powered will be completed in the Stage I analysis, and no new analyses based on primary efficacy endpoint will be made at the end of the study. Therefore, no further multiplicity adjustment will be applied.

The Stage II analysis for long-term safety follow-up will be performed after all subjects have completed the study (Week 64). Annualized asthma exacerbation and severe asthma exacerbation data along with other secondary endpoints measured through Week 64 will be analyzed.

It is anticipated that sites in Japan will randomize approximately 15% of the targeted enrollment of 552 subjects. In the event that enrollment of the Japanese subjects is delayed, and to ensure a timely Stage I analysis, non-Japanese sites may be permitted to continue to enroll subjects to reach the required sample size for the Stage I analysis. In this event, sites in Japan may continue to enroll until such time as approximately 15% of the targeted enrollment of 552 subjects has been enrolled while non-Japanese sites will be closed. Subgroup analysis of the Japanese subjects for the Stage I analysis will be conducted with available Japanese subjects who have completed the Week 52 visit.

There will be an interim analysis after approximately 552 subjects have completed the Week 28 visit. All data available at that time would be analyzed as part of the interim analysis. The objective of this interim analysis is to accelerate decisions on future development options for MEDI9929. Regardless of the interim analysis results, the study will be continued and completed. As a result, no alpha will be spent at the interim analysis. The interim analysis result may be used to accelerate planning for subsequent studies. Details related to unblinding for the interim analysis are in Section 4.6.2.3.

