4.1.7 Replacement of Subjects

Subjects in this study will not be replaced.

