4.8.2 Sample Size and Power Calculations

Sample size calculations have been performed for the primary endpoint of annualized AER, based on the negative binomial distribution (Keene et al, 2007). Approximately 552 subjects will be randomized in the study, with approximately 85% of the total number of subjects designated as non-Japanese subjects (ie, subjects enrolled at sites outside of Japan) and approximately 15% of the total number of subjects designated as Japanese subjects (ie, subjects enrolled at sites in Japan). The total enrollment may exceed 552 subjects depending on whether additional non-Japanese subjects are enrolled to mitigate for slow enrollment in Japan, and to accommodate subjects in screening/run-in when the different strata are closed to enrollment.

Subjects will be randomized in a 1:1:1:1 ratio to receive one of 3 dose levels of SC MEDI9929 (280 mg Q2W, 210 mg Q4W, or 70 mg Q4W) or placebo Q2W for 52 weeks. Prior to randomization, subjects will be stratified by study site (non-Japanese and Japanese) and then by blood eosinophil count (\geq or< 250 cells/ μ L) and ICS dose level (medium or high). Subjects taking maintenance OCS will be automatically assigned to the high-dose ICS strata. At least 50% of the total subjects will be enrolled in the high blood eosinophil stratum (\geq 250 cells/ μ L), and at least 40% of the subjects in each blood eosinophil stratum will be receiving high-dose ICS. Details on the 8 strata (4 strata for non-Japanese subjects and 4 identical strata for Japanese subjects) are included in Section 3.1.1.

The primary analysis will be based on the ITT population. The 3 primary comparisons are as follows: MEDI9929 280 mg Q2W versus placebo; MEDI9929 210 mg Q4W versus placebo; and MEDI9929 70 mg Q4W versus placebo. A total of 124 subjects per treatment group would be required to detect a 40% reduction in the annual AER for each MEDI9929 dose group compared to placebo group, assuming an AER of 0.7 in the placebo group, a two-sided significance level of 0.1, 80% power, and a dispersion parameter of 0.7 based on the negative binomial distribution. The AER of 0.7 in the placebo group was estimated based on internal and external studies with a similar subject population (before considering dropouts). The dispersion parameter of 0.7 was selected from the mepolizumab study in subjects with severe, eosinophilic asthma (Pavord et al. 2012). Sample size was increased to 138 per

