treatment group to accommodate a 10% loss of information due to dropouts. The minimal detectable difference is approximately 28% reduction in annual AER. Figure 4.8.2-1 provides power calculations based on varying sample sizes for a selected treatment effect of AER reduction of 40% and 50%. The minimum acceptable reduction in the annual AER of 40% for the study population was based upon an expected reduction of approximately 50% in a Th2-driven asthma population which appears to be achievable in competitors which target Th2 cytokines (eg, IL-13, IL-5) and a more modest reduction in a non-Th2 asthma population for which there are little data and no current competitors.

[figure not shown]

Figure 4.8.2-1 Power Calculations for an Annual Asthma Exacerbation Rate of 40 Percent or 50 Percent

AER = asthma exacerbation rate; AERR =asthma exacerbation rate reduction; yr = year Note: The sample sizes do not reflect the projected dropout rate.

It is generally recommended that Japanese subjects be included in studies to identify interethnic differences in the dose-response relationship early in clinical development. The target percentage of Japanese subjects for inclusion in this study is approximately 15% of the targeted enrollment of 552 subjects. A subgroup analysis of the non-Japanese subjects and Japanese subjects will be performed. Due to a small sample size, the subgroup analysis of the

Japanese subjects will not have sufficient power to detect differences with statistical significance.

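### The Stage I and interim triggers use the number randomized (about 552) as a count of completers, and the Stage I Japanese subgroup is restricted to Week 52 completers although the primary model is ITT

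*Protocol*

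**What the plan says.** **Size.** Section 4.8.2: "Approximately 552 subjects will be randomized in the study". The same section starts from 124 per group ("A total of 124 subjects per treatment group would be required to detect a 40% reduction in the annual AER") and raises this to 138 per "treatment group to accommodate a 10% loss of information due to dropouts". Section 4.1.7: "Subjects in this study will not be replaced".

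**Triggers.** Section 4.8.7 (repeated in the synopsis): "The Stage I analysis will be conducted after approximately 552 subjects have completed the Week 52 visit". For the interim (also in the synopsis and Section 3.1.1): "There will be an interim analysis after approximately 552 subjects have completed the Week 28 visit".

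**Over-enrolment.** The synopsis and Sections 3.1.1 and 4.8.2 let enrolment exceed 552 for two reasons: slow enrolment in Japan, and subjects already in screening when strata close. Dropout is not among them.

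**Analysis set.** Section 4.8.3.1 puts the primary analysis on the ITT population (randomized and given any product, Section 4.8.1), with follow-up time as an offset. Section 4.8.7 says that Stage I uses all efficacy and safety data collected through Week 52.

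**Japanese subjects.** At Stage I their subgroup analysis "will be conducted with available Japanese subjects who have completed the Week 52 visit". Section 4.8.7 also says that "no new analyses based on primary efficacy endpoint will be made at the end of the study". Stage II reports exacerbations through Week 64.

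**The concern.** One number does two jobs. A total that was enlarged because some follow-up will be lost cannot, without further enrolment, also be the number who reach Week 52. The protocol is also not consistent about how Stage I is sized. The synopsis and Section 3.1.1 speak of the required number being enrolled for Stage I, and Section 4.8.7 itself speaks of enrolling up to the required Stage I sample size, but its trigger counts completed visits.

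If the count is not reached, the protocol does not say when the data for the only powered analysis are cut. Someone must then choose a date, by which time interim results exist.

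The Japanese rule is a separate matter. Completing Week 52 is a post-randomization event that may relate to treatment or to asthma control. Restricting the subgroup to completers gives it a different basis from the primary analysis it is meant to be compared with, and discards follow-up that the offset model can use.

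**Working it through.** **1. Reproduce the plan's sample size.** Inputs from Section 4.8.2: placebo rate 0.7 per year, 40% reduction (active rate 0.42), dispersion 0.7, two-sided alpha 0.1, power 80%. One year of follow-up is taken.

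n per group = (z₀.₉₅ + z₀.₈₀)² × [(1/0.7 + 0.7) + (1/0.42 + 0.7)] / (ln 0.6)² = 123.4, rounded up to 124.

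Inflation: 124 / 0.9 = 137.8, rounded up to 138; 4 × 138 = 552. The stated figures reproduce exactly, so 552 is a randomized total that already contains the dropout allowance.

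**2. Completers from 552 randomized.** The protocol gives a 10% loss of information, not a share missing Week 52. Reading it as 10% non-completion is an assumption, so a range is shown. Completers = 552 × (1 − d); number to randomize for 552 completers = 552 / (1 − d), rounded up.

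| Not reaching Week 52 (d) | Completers from 552 | Randomized needed for 552 completers |
|---|---|---|
| 5% | 524 | 582 |
| 10% | 497 | 614 |
| 15% | 469 | 650 |
| 20% | 442 | 690 |

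At 10% the shortfall is 552 − 497 = 55. The 20% row would apply if dropout were spread evenly over the year, since each leaver then loses half a year on average (20% × 0.5 = 10% of person-time). The protocol does not state that pattern. The protocol gives no loss figure for Week 28, so the interim shortfall cannot be sized, but the mismatch is of the same kind.

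**3. Permitted over-enrolment.** Japanese target: 0.15 × 552 = 82.8, about 83. In the extreme contingency 552 non-Japanese plus 83 Japanese subjects are randomized, 635 in all, giving 635 × 0.9 = 571.5 completers. The trigger is then reachable. But the 552 non-Japanese subjects supply only about 497, so about 55 of the completers would have to be late Japanese subjects. Section 4.8.7 allows this contingency so that Stage I is not delayed by Japan.

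**4. Japanese subgroup.** Per arm: 82.8 / 4 = 20.7. At 10% non-completion: 82.8 × 0.9 = 74.5 completers, or 18.6 per arm. The completer rule therefore removes about 2 of about 21 per arm, before any effect of late enrolment.

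**5. Week 64 against Week 52.** The last dose is at Week 50 (Section 3.1.1). The Week 52 endpoint already contains two weeks after it, so the Stage II rate adds 64 − 52 = 12 weeks of post-treatment follow-up.

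**The case against.** The case for leaving the text alone has real substance.

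- Both triggers say approximately, and enrolment may exceed 552. Subjects who stop product are encouraged to attend through Week 64 (Section 4.1.6), so the share missing Week 52 could be below 10%. A reader might infer that the trigger can never be met; the documents support that only for the planned 552, not under every permitted over-enrolment. Still, a gap of about 10% is wide for an approximate count, and nothing in the plan enrols extra subjects for dropout.
- A reader might infer that the primary result is biased or underpowered. It is not: Stage I uses all data through Week 52 on the ITT population with an offset. If the count were missed, waiting until everyone has finished would introduce no bias.
- A reader might infer that the cut can be steered by interim results. Section 4.6.2.3 confines the interim and Stage I analyses to limited sponsor personnel not directly involved in conduct. No inference is made at the interim and the study continues regardless. What remains is that the date is not fixed by the text.
- A reader might call the Japanese subgroup selected on outcome. Selection is on attending Week 52, not on exacerbations. The sentence closes a paragraph on delayed enrolment, so it is partly an administrative cut; late enrollees cannot have Week 52 data at Stage I under any rule. As worded, though, it also excludes early withdrawals.
- A reader might infer that the Week 52 rate in the full Japanese set will never be analyzed. The bar on new primary-endpoint analyses serves error control, and Sections 3.2.2, 4.8.2 and 4.8.3.4 promise a Japanese subgroup analysis without tying it to Stage I. The execution may be in the SAP. The protocol simply does not say how late enrollees are handled for Week 52.
- The subgroup is acknowledged to be underpowered (Section 4.8.2), so two subjects per arm do not change its precision much.

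**Conclusion.** The concern holds in two limited parts.

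First, the Stage I and interim triggers state a completer count that the planned enrolment does not deliver. On the assumption of 10% non-completion the Stage I shortfall is about 55 subjects; over 5% to 20% non-completion it runs from about 28 (552 − 524) to about 110 (552 − 442). The consequence is an unclear date and definition of the data cut. The primary estimate, alpha and power do not change.

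Second, the Stage I Japanese subgroup conditions on completing Week 52 and drops early withdrawals whom the primary ITT model retains, about 2 of about 21 per arm at 10%. The direction of any bias is unknown. Claims that the trigger is impossible in all circumstances, or that the subgroup is chosen on outcome, go beyond the text. This is a clarification to make before the cut is taken, not a threat to the primary inference.

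**What to change.** In Section 4.8.7 and the synopsis (and Section 3.1.1 for the interim):

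1. Define the Stage I cohort as the first approximately 552 subjects randomized and dosed. Trigger Stage I when every subject in it has completed Week 52 or left the study earlier. Define the interim the same way at Week 28.
2. Run the Stage I Japanese subgroup on all randomized and dosed Japanese subjects in that cohort, dropouts included, with follow-up time as the offset.
3. If Japanese enrolment is late, report the Week 52 exacerbation rate for all Japanese subjects at Stage II as a descriptive subgroup analysis without alpha. Add a clause so that the bar on new primary-endpoint analyses does not exclude it. The full-ITT primary analysis need not be repeated; the protocol deliberately avoids a second primary result.

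The cost is a few sentences and, only if Japan is late, one additional descriptive table. Sample size, alpha and power stay as they are.

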4.8.8 Data and Safety Monitoring Board

An independent DSMB will perform evaluations of safety data at specified regular intervals throughout the study and make recommendations to the sponsor regarding further conduct of the study. Information regarding unblinding for DSMB members is in Section 4.6.2.4. After reviewing the data by treatment group, the DSMB may request that a treatment group be unblinded for additional review. The DSMB does not include any investigators in this clinical study, and will include 4 voting members, 3 of whom are physicians with experience in respiratory diseases and in the diagnosis and management of asthma and 1 biostatistician. Specific details about the DSMB will be included in an external charter.

5 ASSESSMENT OF SAFETY

5.1 Definition of Adverse Events

The ICH Guideline for Good Clinical Practice E6(R1) defines an AE as:

Any untoward medical occurrence in a patient or clinical investigation subject administered a pharmaceutical product and which does not necessarily have a causal relationship with this treatment. An AE can therefore be any unfavorable and unintended sign (including an abnormal laboratory finding), symptom, or disease temporally associated with the use of a medicinal product, whether or not considered related to the medicinal product.

An AE includes but is not limited to any clinically significant worsening of a subject's preexisting condition. An abnormal laboratory finding (including ECG finding) that requires an action or intervention by the investigator, or a finding judged by the investigator to represent a change beyond the range of normal physiologic fluctuation, should be reported as an AE.

Adverse events may be treatment emergent (ie, occurring after initial receipt of investigational product) or nontreatment emergent. A nontreatment-emergent AE is any new sign or symptom, disease, or other untoward medical event that begins after written informed consent has been obtained but before the subject has received investigational product.

Elective treatment or surgery or preplanned treatment or surgery (that was scheduled prior to the subject being enrolled into the study) for a documented pre-existing condition that did not worsen from baseline is not considered an AE (serious or nonserious). An untoward medical event occurring during the prescheduled elective procedure or routinely scheduled treatment should be recorded as an AE or SAE.

5.2 Definition of Serious Adverse Events

An SAE is any AE that:

- Results in death
- Is immediately life-threatening
- Requires inpatient hospitalization or prolongation of existing hospitalization
- Results in persistent or significant disability/incapacity
- Is a congenital anomaly/birth defect in offspring of the subject
- Is an important medical event that may jeopardize the subject or may require medical intervention to prevent one of the outcomes listed above

Medical or scientific judgment should be exercised in deciding whether expedited reporting is appropriate in this situation. Examples of medically important events are intensive treatment in an ED or at home for allergic bronchospasm, blood dyscrasias, or convulsions that do not result in hospitalizations; or development of drug dependency or drug abuse. In addition, any event of confirmed TB that requires treatment (inpatient or outpatient treatment by a health care provider) should be considered an SAE and reported to MedImmune Patient Safety (see Section 5.5).

For this study, AESIs that require rapid reporting (see Section 5.5) include anaphylactic reactions (see Appendix 2 for guidance for anaphylaxis diagnosis), confirmed immune complex disease (Type III hypersensitivity reactions), and malignancy. The rapid reporting of AESIs allows ongoing analysis of these events in order to characterize and understand them in association with the use of this investigational product.

5.3 Definition of Adverse Events of Special Interest

An adverse event of special interest (AESI) is one of scientific and medical interest specific to understanding of the investigational product and may require close monitoring and rapid communication by the investigator to the sponsor. An AESI may be serious or non-serious.

For this study, AESIs that do not require rapid reporting (see Section 5.4.3) include helminth infections, serious infections with special attention to respiratory infections, and injection site reactions that are not considered TESAEs. These AEs should be recorded in the eCRF once a diagnosis is confirmed, and will require additional data collection on the eCRF, but will not require rapid communication to MedImmune.

